4.6.8 Other Safety Assessments - AESI

4.6.8.1 Definitions and Derivations

For specification of MedDRA version and collection of AEs see section 4.6.2.

AESI categories will be classified using PT list for the following safety topics:

- New diagnosis of CCI or CCI of the existing CCI condition
- CCI or worsening of CCI
- CCI
- CCI
- CCI
- CCI

Objective measurement for CCI

Objective measurement of CCI is defined as a CCI of CCI in CCI or a CCI of CCI in CCI within CCI, i.e. this will not be classified using SOC or PT.

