8.4.4 AEs Based on Examinations and Tests

Deterioration as compared to baseline in protocol-mandated laboratory values, vital signs, and ECGs should only be reported as AEs if they meet any of the following:

- fulfil any of the SAE criteria
- are the reason for discontinuation of the IMP
- are clinically relevant as judged by the investigator (which may include, but is not limited to, consideration as to whether intervention or non-planned visits were required or other action was taken with the IMP, eg, drug interruption).

If deterioration in a laboratory value/vital sign is associated with clinical signs and symptoms, the sign or symptom will be reported as an AE and the associated laboratory result/vital sign will be considered as additional information. Wherever possible, the reporting investigator uses the clinical, rather than the laboratory term (eg, anaemia vs low haemoglobin value). In the absence of clinical signs or symptoms, clinically relevant deteriorations in non-mandated parameters should be reported as AEs (Section 8.4).

Any new or aggravated clinically relevant abnormal medical finding at a physical examination as compared with the baseline assessment will be reported as an AE.

The results from the protocol-mandated laboratory tests and vital signs will be summarised in the CSR.

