8.4.6 Adverse Events of Special Interest

Additional monitoring and data collection will be performed during the study for the following safety events classified as AESI, based on the CCI [REDACTED] identified for zibotentan in oncology clinical studies conducted previously, as CCI [REDACTED] of both zibotentan and dapagliflozin (eg, CCI [REDACTED]), and CCI [REDACTED] associated with the use of dapagliflozin:

- New diagnosis of CCI [REDACTED] or CCI [REDACTED] of the existing CCI [REDACTED] condition. Any CCI [REDACTED] CCI [REDACTED] suggestive of CCI [REDACTED] should be properly assessed by the investigator, to ensure timely and proper management of the participant's condition.
- CCI [REDACTED] or worsening of CCI [REDACTED] (eg, CCI [REDACTED] CCI [REDACTED] of any CCI [REDACTED], etc).
- CCI [REDACTED] defined as a CCI [REDACTED] of CCI [REDACTED] mmHg in CCI [REDACTED] or a CCI [REDACTED] of CCI [REDACTED] mmHg in CCI [REDACTED] within CCI [REDACTED]. Participants will be educated about the symptoms of CCI [REDACTED] and participants with CCI [REDACTED] or CCI [REDACTED] will be provided with a CCI [REDACTED] and asked to contact the investigator if symptoms occur or if their CCI [REDACTED] is CCI [REDACTED] mmHg.

- **CCI** [REDACTED]. In the event of symptoms of **CCI** [REDACTED], a **CCI** [REDACTED] **CCI** [REDACTED] should be performed.
- **CCI** [REDACTED].
- **CCI** [REDACTED], including the following: increase in **CCI** [REDACTED] by **CCI** [REDACTED] mg/dL (**CCI** [REDACTED] μ mol/L) within 48 hours; or increase in **CCI** [REDACTED] to **CCI** [REDACTED] which is known or presumed to have occurred within the prior 7 days (or using the last available value of outpatient **CCI** [REDACTED] within 3 months as the baseline value); or **CCI** [REDACTED] **CCI** [REDACTED] mL/kg/h for 6 hours.

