4.6.8.2 Presentations

AEs of special interest

Number of subjects with an AESI will be presented by event category and by PT within the event category. Event count table will also be presented. Key subject information for subjects with AESI will be presented.

Objective measurement for CCI

Number and percentage of subjects who met objective measurement for CCI will be presented by treatment group.

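### The protocol defines its last AESI by measurement, but the SAP counts it only from preferred terms, so qualifying values that no one reports as an AE are missing from the AESI table

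*SAP*

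**What the plan says.** Protocol 8.4.6 lists six AESIs. Two carry numeric definitions. One is in mmHg. The other, the last in the list, has three limbs:

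- a rise of a stated amount, "mol/L) within 48 hours; or increase in" (the second limb follows);
- a rise to a stated level, "which is known or presumed to have occurred within the prior 7 days", where the last available outpatient value "within 3 months as the baseline value" may be used instead;
- a threshold of a stated "mL/kg/h for 6 hours".

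The name, analyte and limits are redacted. The units and time limits are not.

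Protocol 8.4.4 covers deterioration in mandated laboratory values, vital signs and ECGs. These "should only be reported as AEs if they meet any of the following": a seriousness criterion, being the reason for discontinuing study drug, or clinical relevance in the investigator's judgement.

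SAP 4.6.8.1 sets the counting rule for all six topics: "AESI categories will be classified using PT list for the following safety topics". It then adds one objective measurement and says of it "i.e. this will not be classified using SOC or PT". SAP 4.6.8.2 describes the output: "Number of subjects with an AESI will be presented by event category and by PT within the event category". A separate count is given for that one objective measurement.

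**The concern.** A preferred-term list can find only what an investigator has entered as an adverse event. The protocol defines this AESI by values, yet its reporting rule does not require every such value to be entered. The table may therefore count fewer participants than meet the protocol's own definition, and how many are missed may differ between sites.

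This is a safety study in cirrhosis. If the units do point to kidney injury, the topic is central to it: recent acute kidney injury is an exclusion (protocol 5.2), a confirmed eGFR below 45 mL/min/1.73 m² is among the reasons for discontinuing study drug (7.1), and lower kidney-injury risk through less diuretic use is part of the rationale (2.1). With about 22 participants per arm, a difference of one or two AESIs will be noticed, so it should be clear what the count contains.

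**Working it through.** There is no plan figure to reproduce. The check is a comparison of text, with arithmetic only for size and feasibility.

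**1. The two numerically defined AESIs side by side**

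| | AESI defined in mmHg | Last AESI in the list |
|---|---|---|
| Protocol 8.4.6 | limits in mmHg within a set time | mg/dL within 48 hours; rise within 7 days or against a 3-month outpatient value; mL/kg/h for 6 hours |
| Instruction to report once measured | protocol 8.3.2: a finding confirmed in the vital-sign test is to be reported as an AESI (name redacted, refers to 8.4.6) | none found; the three conditions of 8.4.4 apply |
| SAP 4.6.8.1 classification | preferred-term list | preferred-term list |
| SAP count from measured values | yes (4.6.8.1, 4.6.8.2) | none |

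The name of the SAP's objective measurement is redacted too. Its sentence has the two-part form of the mmHg definition and none of the 48-hour, 7-day or mL/kg/h elements, so it is not the last AESI.

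**2. Does another table count these participants?** SAP Table 9 includes creatinine, eGFR and eGFR2. The treatment-emergent criteria in 4.6.3.1 cover platelets, NT-proBNP, ALT, AST, ALP, direct and total bilirubin and INR. The shift tables cover the same parameters without INR. There is no creatinine or eGFR threshold, although protocol 9.4.3.3 leaves criteria for relevant laboratory parameters to the SAP. The additional key subject information and individual graphs in 4.6.3.2 concern liver safety. Renal values appear in by-visit descriptive summaries, in listings, and in the eGFR change model (4.2.10.4).

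**3. Size.** Planned number per arm: 22 (protocol 9.2). One uncounted participant: 1/22 = 0.045, or 4.5 percentage points of that arm's AESI rate. Nothing in the documents gives the number of such participants.

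**4. Which limbs can be derived from scheduled samples?** Safety chemistry is taken at every visit (protocol Table 1). From Day 1 the nominal days are 1, 8, 15, 22, 43 and 57, so the gaps are 7, 7, 7, 21 and 14 days. With the visit windows:

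- Visit 3 (Days 5–11) to Visit 4 (Days 12–18): 12 − 11 = 1 day at the shortest. Visit 4 to Visit 5 (Days 19–25): 19 − 18 = 1 day.
- Visit 5 to Visit 6 (Days 38–48): 38 − 25 = 13 to 48 − 19 = 29 days.

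The 48-hour limb is thus assessable only when two visits fall at opposite edges of adjoining windows, or from unscheduled samples. The second limb can be assessed around Weeks 1 to 3 on the 7-day wording, and at later visits through the 3-month outpatient reference. A Day 1 value is still within 3 months at Visit 7 (latest Day 60: 60 − 1 = 59 days). The mL/kg/h limb has no scheduled collection in Table 1 and can come only through AE reporting.

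**The case against.** The case on the other side has several sound parts.

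- A reader might infer that these values disappear, or that group means hide a few large individual changes. The documents do not support that. SAP 4.6.3.2 summarises every Table 9 parameter by visit, as value and change, with the section 3.3 statistics, which include minimum and maximum. Listings show each participant's values, changes and abnormalities. What is missing is a count of participants who meet the definition.
- A reader might infer that participants stopped for low eGFR are missed. They are not: under 8.4.4 a value that is the reason for discontinuing study drug is reportable as an AE, and SAP 4.6.2.2 tabulates AEs leading to discontinuation with key subject information.
- A reader might infer that the AESI rate rests on investigator judgement and not on the definition. That goes too far. Section 8.4.6 classifies these events as AESIs and calls for extra monitoring and data collection, so an investigator may report every qualifying value, and the preferred-term list would then capture it. The loss is confined to values that are not reported.
- Blood pressure is measured supine and standing at every visit, so the mmHg definition suits direct derivation better than this one. That explains part of the difference in treatment. It does not cover the second limb, for which chemistry is available at every visit.
- A fixed pre-dose baseline is not the protocol's reference. Section 8.4.6 speaks of the last available outpatient value, which from Week 2 may be the previous visit's. A fixed baseline could flag slow cumulative change. This stands, and the reference must be stated.

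The study is double-blind, which makes under-reporting that differs by arm less likely. The main cost is lower sensitivity and uneven ascertainment.

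**Conclusion.** The mismatch is in the text and redaction does not explain it. Protocol 8.4.6 defines this AESI by measurement, 8.4.4 permits a qualifying value to go unreported, and the SAP counts only what is reported. Any participant lost in this way is absent from the AESI tables and from the AESI line of the overall AE summary, but not from the laboratory summaries and listings.

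The number affected is unknown and cannot be estimated with the limits redacted; each one is worth 4.5 points in an arm of 22. That the analyte is creatinine is an inference from the units. The counting gap does not depend on it, but the statements about creatinine and eGFR tables and the renal importance do. This is a cheap improvement to safety ascertainment. It does not show that the AESI table will be wrong.

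**What to change.** **SAP 4.6.8.1.** Add a supportive objective measurement for this AESI, parallel to the one for the mmHg-defined AESI:

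- apply the limits already in protocol 8.4.6, unchanged, to all scheduled and unscheduled laboratory values;
- state the reference value in line with 8.4.6, that is, the last available outpatient value within 3 months; if the pre-dose baseline is also used, label that result separately;
- state that the 48-hour limb is rarely assessable from scheduled samples and that the mL/kg/h limb comes only through AE reporting.

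**SAP 4.6.8.2.** Present number and percentage by arm next to the preferred-term count, not in place of it.

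**Protocol 8.4.4 and 8.4.6.** Reconcile the two sections on whether a value that meets an AESI definition is to be reported as one.

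**Cost.** One derived flag and one table from data already collected, plus a clarifying sentence in the protocol. The count may be higher in any arm than the preferred-term count, and the two will need to be read together. If the sponsor prefers not to derive it, the least that is needed is a statement in the SAP that this AESI is counted from investigator reports only.

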4.6.8.2 Presentations

AEs of special interest

Number of subjects with an AESI will be presented by event category and by PT within the event category. Event count table will also be presented. Key subject information for subjects with AESI will be presented.

Objective measurement for CCI

Number and percentage of subjects who met objective measurement for CCI will be presented by treatment group.

4.6.9 Other Safety Assessments - To assess liver safety

4.6.9.1 Definitions and Derivations

Modified Hy's Law

AEs that are cases of modified Hy's law will be identified based on preferred term.

4.6.9.2 Presentations

The number and percentage of subjects with event will be tabulated by treatment group

5 INTERIM ANALYSIS

No interim analysis is planned. For information about the DMC safety monitoring during the study see DMC Charter.

7 APPENDIX

Not applicable.
